to whom serious and unexpected adverse events will be reported. The plan will help ensure the safety of all participants. The PI will communicate via electronic submission to the IRB all unanticipated problems as defined by the IRB and all serious adverse events (SAEs) to the medical investigator within 72 hours.

The investigators will monitor the study's conduct. Study staff will report adverse events or other problems directly to the PI as they occur. The PI will schedule monthly meetings with study staff to review data on adverse events and recruitment or adherence to regimen problems. Any significant health problems coming to our attention during the study will be referred to the participant's usual source of medical care with his/her permission. We will cooperate fully with his/her physician by providing relevant medical records. The following criteria, if detected during any part of the study regimen, will lead to referral to the participant's usual source of medical care:

- Clinical symptoms or signs of CVD include chest pain suggestive of angina pectoris, unusual dyspnea on exertion, severe ankle edema, and symptoms suggestive of transient ischemic attacks or intermittent claudication.
- Musculoskeletal injuries or problems causing severe pain during exercise or interference with daily activities.

A. Adverse Events

Adverse events that occur will be classified as a Serious Adverse Event (SAE) or an Adverse Event (AE). Serious adverse events are defined to include:

- Death
- A life-threatening event
- Severe illness, including worsening of a pre-existing condition, injury, or accidents
- An inpatient hospitalization, surgical procedure, or treatment to prevent an SAE
- A permanent disability or incapacity
- A clinically significant abnormal laboratory or diagnostic test result
- Any other event that, in the opinion of the principal investigator or study physician, might have resulted in a serious adverse event if medical intervention had not been initiated

Serious adverse events will be reported to the study PI, Project Manager, and MI throughout the trial. Serious adverse events will be collected from randomization until the final visit. SAE data will be analyzed quarterly, but serious or life-threatening adverse events require immediate reporting and follow-up in the event that an adverse event occurs on campus and results in a serious or life-threatening situation, the investigator or other project staff present will begin emergency measures, as appropriate, and call 911.

- For minor physical injury, the individual will be encouraged to see a health care practitioner of his or her choice.
- If the study participant experiences psychological or emotional distress, the project staff will cease research activities and attempt to calm and reassure the participant. The participant will be directed to an appropriate healthcare practitioner for further assessment and treatment as needed.
- The investigator and/or project staff will record detailed narrative notes describing the adverse event they witnessed or that was reported by the participant. The medical investigator will complete the Notification form for a Serious Adverse Event.

Serious adverse event reporting will follow the requirements of the IRB of the Pennington Biomedical Research Center. Serious adverse events that are unanticipated problems will be reported within 48 hours.

For this trial's purposes, an **adverse event** is defined as any health-related unfavorable or unintended medical occurrence that happens after randomization. Examples of Adverse Events include but are not limited to the following:

- An event that requires a visit to a physician because it alters the participant's ability to do physical activity
- An event that occurs as a result of a study procedure which is not listed in the risks section of the consent

Adverse events will be reported to the study PI and the MI throughout the trial as necessary. Adverse event data will be collected from randomization until the final visit. Adverse events classified as serious will be reported from the date of consent through the final closeout visit. Adverse event data will be analyzed quarterly, but serious or life-threatening adverse events require immediate reporting and follow-up. It is anticipated that most adverse events will be mild, and the participant will be able to resume intervention activities within a week of reporting the event.

B. Stopping Rules

There is minimal risk for participating in this trial. The most likely scenario that would indicate a cessation of the study would be a failure to recruit participants or implement the intervention as planned. Nevertheless, in addition to monitoring recruitment and compliance with the intervention, the staff will monitor the participant rates of injury. The medical investigator, in conjunction with the study investigators, will alert the IRB and funder if a larger than reasonably expected injury rate occurs in the treatment groups.

Other issues that are related to the stopping rules include:

- New information – It is unlikely that new information will become available during this study, which would result in the discontinuation of the trial.
- Limits of assumption – It is possible that the value of data analysis will be limited by differences between the intervention groups because of study dropouts or missing data.
- Limit of rules – We acknowledge that circumstances other than what is listed may justify stopping the study.

Withdrawal of Subjects

There is no risk associated with withdrawal from the study. Participants may voluntarily withdraw or be withdrawn from the study if either the PI or MI feels that their continued participation would compromise the participant's safety or the results of the study.

Risks to Subjects

The following is a list of reasonably foreseeable risks, discomforts, hazards, or inconveniences to the subjects related to the procedures in this study:

OGTT: There is a possibility of pain, bruising, or infection at the site of the needle insertion for the IV line. Trained personnel minimize this risk. The drink may cause nausea, vomiting, abdominal bloating, or a headache.

DXA: The amount of radiation used for this procedure is very small. The radiation dose for this scan is equivalent to the radiation you are naturally exposed to in the environment in less than one day. Scans will not be performed on any subject who is pregnant. A pregnancy test will be performed within 72 hours before the scan on females of child-bearing potential.

Electrocardiogram (EKG or ECG): There are minimal risks associated with this test. There is a small possibility there may be some redness or irritation while cleaning the skin prior to applying the electrodes or if you happen to be allergic to the adhesive on the electrodes.

Blood Draws: There is the possibility of infection and/or pain and bruising at the vein on your arm where the needle is inserted. Aseptic (sterile) technique and trained personnel minimize these risks.

Submaximal Fitness Assessment: All exercise testing core operating procedures are in accordance with the American College of Sports Medicine's Guidelines for Exercise Testing and Prescription, as well as the American Heart Association. There is minimal risk of injury or a cardiovascular event during exercise testing. We believe the risk of an event during exercise testing is minimized with a pretest review of the medical history, physical examination, use of highly trained staff, and well-defined emergency procedures. Participants may experience temporary discomfort during blood pressure recordings due to the pressure of the blood pressure cuff on the arm. All tests are conducted in the presence of Exercise Testing Core personnel with extensive experience in conducting maximal exercise testing. All laboratory staff

are trained in BLS (basic life support – CPR) and/or ACLS (advanced cardiac life support). In the event of a life-threatening emergency, the subject would be treated with BLS/ACLS by trained individuals and subsequently be transported to the nearest acute care medical-surgical facility via Emergency Medical Services, which is a parish-wide paramedic response unit.

Accelerometry & other activity monitoring devices: There is no known risk associated with measuring activity with accelerometers and other activity monitoring devices. Accelerometers fit comfortably on your waist or arm and can easily be adjusted should they become uncomfortable. In rare cases, the device may irritate the skin. If this should happen, the device can easily be repositioned to be more comfortable.

Blood Pressure Testing: Participants may experience temporary discomfort during blood pressure recordings due to the pressure of the cuff on their arm.

Height measurement: There is no risk to participants who record their height.

Body weight: There is no risk to participants who record their body weight. Measurements will be taken in a secluded area to protect the participant's privacy.

Self-report Questionnaires: There are no anticipated risks from completing self-report questionnaires. If signs of minor stress or fatigue are apparent, participants will be given time to take a break from completing the questionnaires. It is estimated that the questionnaires will take approximately 30 minutes to complete. The questions contained in some of the questionnaires may make people feel uncomfortable. Responses to the questions will be coded to protect confidentiality, and participants may choose not to answer questions.

Exercise interventions: The proposed exercise interventions are unlikely to cause major harm. We have conducted numerous exercise training studies and have never had a serious adverse event. There is the possibility of adverse events ranging from minor musculoskeletal problems to, in very rare cases, cardiovascular events. Exercise bouts will include aerobic exercise in the form of treadmill walking at moderate intensity. The exercise prescription will be at the discretion of the trainer to ensure compliance with the intervention and minimize injury. Occasionally, study participants experience minor orthopedic problems, but most self-correct with rest and standard first aid. These orthopedic injuries will be minimized by gradually progressing participants to their abilities as necessary. Exercise staff are trained in first aid and basic CPR. Each staff member is trained in either advanced or basic life support, and an automated external defibrillator and a fully stocked crash cart are kept on site. Although some study participants will be at moderately elevated risk for CVD, they will receive a thorough health screen, including a physical examination and an EKG. According to the available data on adverse events resulting from exercise, risk should be low. Fatal events during exercise are extremely rare.

Potential Benefits to Subjects

There are no direct benefits to the participants; however, the knowledge to be gained is critical for the advancement of science.

Vulnerable Populations

No vulnerable populations will be included in the study.

Multi-Site Research

This is a single-site research study.

Sharing of Results with Subjects

Subjects will be provided reports of medical information obtained from the body composition and exercise stress test following the completion of the study if requested.

Resources Available

The outpatient and inpatient research units are well-equipped and staffed to carry out the requirements of this study, and appropriate standards of practice are in place to ensure appropriate research procedures are followed.

Setting

This study will be conducted at Pennington Biomedical Research Center.

Compensation

Enrolled participants will be compensated up to \$300 for the completion of the study. Participants will receive \$100 after the completion of baseline and randomization if eligible. Participants will receive up to \$100 for completion of all intervention-related activities (e.g., returning telephone calls, tracking, and adhering to the exercise protocol). The remaining \$100 will be reimbursed upon the completion of the study (defined as providing complete endpoint data measures). Reimbursements may be prorated according to the degree of adherence and willingness of participants to accommodate staff requests. Reimbursement will be requested from the LSU payroll department, and it usually takes about 3-4 weeks for it to arrive at Pennington Biomedical Research Center.

As part of the study, all exercise intervention participants will receive a treadmill for home use. After completing the three-month measures, control group participants will be provided with an in-home treadmill and individualized exercise program similar to that prescribed to the exercise group. As additional compensation for participation in the study, participants will keep the treadmill provided.

Confidentiality

All participants are assured of their confidentiality, both verbally and in the informed consent form. The clinical facilities are strictly limited to the staff of the research institution and to research participants. This is accomplished by a variety of stringent security measures. All medical records are stored in locked areas. Access to these areas is limited to the clinical support staff, the director of the clinical facilities, and the PIs. Participants' medical records are filed according to ID numbers. All forms on the chart display the ID number. Electronic data storage is similarly restricted, with only the PIs and authorized persons having access to databases containing confidential clinical records, i.e., those containing names OR other identifying information.

Data, including body weight, body composition, exercise testing, etc., will be collected from participants. Data are confidentially collected from study participants and are only used for research purposes. All records are kept in locked file cabinets, and participant data can be identified only by number. Data are used only in aggregate, and no identifying characteristics of individuals are published or presented.

Provisions to Protect the Privacy Interests of Subjects

All attempts will be made to maintain a subject's privacy. Safeguards such as password-protected computers and networks have been put in place to limit access to subject data. Subjects will be given ample time to read over the consent, ask questions, and agree to participate in the research study. Subjects may decline to answer questions they are not comfortable with. Each procedure will be explained to the subject before it is performed. All discussions will be held with study subjects in examination or private rooms to protect their privacy.

Compensation for Research-Related Injury

No form of compensation for medical treatment or for other damages (i.e., lost wages, time lost from work, etc.) is available from the Pennington Biomedical Research Center. In the event of injury or medical illness resulting from the research procedures in which a subject participates, they will be referred to a treatment facility. Medical treatment may be provided at the subject's expense or at the expense of their health care insurer (e.g., Medicare, Medicaid, Blue Cross-Blue Shield, Dental Insurer, etc.), which may or may not provide coverage. The Pennington Biomedical Research Center is a research facility and provides medical treatment only as part of research protocols. Should the study subject require ongoing medical treatments, they must be provided by community physicians and hospitals.

Economic Burden to Subjects

All study-related tests and procedures will be at no cost to the subject. The subject will incur transportation costs to and from PBRC.

Consent Process

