Protocol Title: The Exercise And Colorectal Cancer Treatment (EXACT) Trial

PI Name: [name]

Sub-Investigator's Name: [name]; [name]

Medical Investigator: [name]

Study-site contacts: [name]; [name]; [name]; [name]; [name]; [name]

Protocol Version Date: March 27, 2024 (Version 13)

Objectives

This randomized trial will examine the biological effects of 12 weeks of moderate-intensity aerobic exercise versus wait-list control in 60 subjects who have completed standard medical therapy for stage I- III colorectal cancer. The primary objective is to determine if aerobic exercise can reduce systemic inflammation, quantified using plasma concentrations of high-sensitivity C-reactive protein and interleukin-6. The secondary objectives are to determine if exercise can reduce 1) insulin resistance quantified using an oral glucose tolerance test and 2) circulating tumor cells quantified using a microfluidic antibody-mediated capture platform. The exploratory objective is to determine if exercise can improve mitochondrial respiration rates and fatty acid oxidation from peripheral blood mononuclear cells, and tumor fraction.

Background

Colorectal Cancer Prognosis. Each year, 145,600 people are diagnosed with colorectal cancer in the United States.¹ Despite efficacious surgical and chemotherapeutic interventions, 25–30% of patients will experience recurrent and metastatic disease within three years of diagnosis, and 91% of those who recur within three years die by five years.² Additional therapies are critically needed to maximize the likelihood of cure for these patients. One such additional therapy may be the prescription of physical activity.³

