We will begin with three months of strict eligibility criteria (Phase 1). At the end of three months, if six subjects are not accrued, eligibility criteria will be expanded for another three-month period (Phase 2). If, at the end of six months, we have still not accrued an average of two subjects per month, we will further expand eligibility criteria (Phase 3). We successfully implemented these prospectively specified stepped inclusion and exclusion criteria in the pilot study.⁴⁸

Phase 1 (most strict) inclusion criteria:

- 1.1 Age ≥18 years
- 1.2 Histologically-confirmed stage III colorectal cancer
 - a. Self-report during screening is acceptable if confirmed with pathology report, state tumor registry file, or physician documentation prior to randomization
- 1.3 Completed surgical resection within 1–24 months or completed chemotherapy (if applicable) within 1-24 months
- 1.4 Provide written approval by a physician or other qualified healthcare provider
- 1.5 No planned major surgery during the study period (including colostomy reversal; however, chemotherapy infusion port removal is permitted)
- 1.6 Readiness to exercise [as determined by a modified version of the Physical Activity Readiness Questionnaire (PAR-Q)]
 - a. If there are any indications that home-based exercise would be unsafe based on the PAR-Q, the patient will not be enrolled until approval from the patient's provider (e.g., oncologist, cardiologist) confirms that it is safe to exercise
- 1.7 Allow the collection and storage of specimens and data for future use
- 1.8 Willing to be randomized

Phase 2 (less restrictive) inclusion criteria will expand:

- 2.1 Histologically-confirmed stage to include stage I, II, or III colorectal cancer

- a. Self-report during screening is acceptable if confirmed with tumor registry, pathology report, or physician documentation prior to randomization
- 2.2 Time since completing surgical resection to 1–36 months or time since completing chemotherapy (if applicable) to 1-36 months

Phase 3 (least restrictive) inclusion criteria will expand:

- 3.1 Time since completing surgical resection \geq 1 month or time since completing chemotherapy (if applicable) \geq 1 month
- 3.2 Histologically confirmed stage I, II, or III colorectal cancer \geq 1 month since completing surgical resection or \geq 1 month since completing chemotherapy and/or radiotherapy

Exclusion criteria for all three accrual phases of recruitment include:

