- 1.1 Evidence of metastatic colorectal cancer (biopsy-proven or radiologic evidence that results in the initiation of local or systemic therapy)
 - a. Elevated tumor markers (e.g., CEA \geq 5 ng/mL), in the absence of an identified lesion(s) on imaging, that is monitored with surveillance only is not considered evidence of metastatic disease
 - b. Lesion(s) classified on imaging as “suspicious” that are monitored with surveillance only are not considered evidence of metastatic disease
- 1.2 Concurrently actively treated other cancers (except non-melanoma skin cancer or in situ cancers)
- 1.3 Currently enrolled in another clinical trial of weight loss, physical activity, or dietary intervention
- 1.4 Current body mass \geq 181 kg
- 1.5 Unable to provide a baseline fasting blood sample
- 1.6 Unable or unwilling to give informed consent
- 1.7 Unable or unwilling to be randomized
- 1.8 Or any other condition that may impede the testing of the study hypothesis or make it unsafe to engage in the exercise program (as determined by the investigative team)

C. Recruitment Methods

Potentially eligible study subjects may be identified and contacted using the Louisiana Tumor Registry and the Gulf South Community Oncology Research Program.

The Louisiana Tumor Registry is part of the Surveillance, Epidemiology and End Results (SEER) Program, funded by the National Cancer Institute. The registry collects and reports high-quality and timely population-based cancer data across the state to support research activities in cancer prevention and control. The Louisiana Tumor Registry Director is [name], MPH, who is a Professor of Epidemiology at the School of Public Health in the Louisiana Health Sciences Center. Potentially eligible subjects will be identified in the Louisiana Tumor Registry (e.g., using tumor codes

affiliated with the diagnosis of colorectal cancer) and contacted using mail and telephone.

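### Wording defect: the *or* in the time-since-treatment criteria lets the resection limb suffice alone, so read literally they admit people still on chemotherapy, contrary to the Objectives

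*Combined protocol and SAP*

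**What the plan says.** The Objectives set the trial in "subjects who have completed standard medical therapy for stage I- III colorectal cancer".

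Section B (Inclusion and Exclusion Criteria) turns this into timing rules for three accrual phases:

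- Phase 1, criterion 1.3: resection 1–24 months ago "or completed chemotherapy (if applicable) within 1-24 months".
- Phase 2, criterion 2.2: "Time since completing surgical resection to 1–36 months or time since completing chemotherapy (if applicable) to 1-36 months".
- Phase 3, criteria 3.1 and 3.2: the same two limbs joined by *or*, at least 1 month, with no upper limit. Only 3.2 mentions radiotherapy ("since completing chemotherapy and/or radiotherapy").

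Among the exclusions, 1.1 concerns metastatic disease. Exclusion 1.2 is the only other one that mentions cancer treatment, and it is limited to "Concurrently actively treated other cancers". Exclusion 1.8 is a general clause left to the investigative team's judgment.

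The Power analysis section stratifies randomization by sex only. The Statistical Analysis section adjusts for the baseline value and sex only.

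**The concern.** The eligibility rules and the stated population disagree. The Objectives require therapy to be finished. The criteria, applied as written, require only that one of two events lies in the window. The qualifier in brackets attaches to the chemotherapy limb and does not make that limb compulsory for someone receiving chemotherapy. The protocol's own 1-month minimum after chemotherapy can be bypassed in the same way.

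Two things are at stake. First, such a participant falls outside the population that the trial says it studies. Phase 1 is restricted to stage III and opens 1 month after resection, and nothing in the timing criterion separates those who have finished treatment from those who have not.

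Second, treatment that runs, starts or stops during the 12 weeks could plausibly move hs-CRP and IL-6 apart from any effect of exercise, which would add variance. This is an assumption, because the documents give no figure for it. The only treatment-response statement in the Background about a trial outcome concerns tumor fraction, an exploratory outcome. Since treatment status is neither a stratification factor nor a covariate, the plan has no means of absorbing such variance.

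**Working it through.** **Step 1: apply the criterion literally.** Let S mean that resection lies in the phase's window and C mean that chemotherapy was completed in that window. The criterion as written is S or C. A rule that matches the Objectives is S if no chemotherapy was given, and C if it was. The windows are 1–24 months (Phase 1), 1–36 months (Phase 2) and at least 1 month (Phase 3). Hypothetical candidates give the same result in all three phases:

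| Candidate | As written | Treatment-completed rule |
|---|---|---|
| Resected 2 months ago, no chemotherapy | meets | meets |
| Resected 10 months ago, chemotherapy ended 3 months ago | meets | meets |
| Resected 30 months ago, chemotherapy ended 24 months ago | meets | meets |
| Resected 3 months ago, chemotherapy ongoing | **meets** | **fails** |
| Resected 8 months ago, chemotherapy ended 0.5 month ago | **meets** | **fails** |

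The two readings part only for people on chemotherapy or less than 1 month past it, which are the people the Objectives and the 1-month minimum would keep out.

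**Step 2: look for a rule elsewhere that closes the gap.**

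- Exclusion 1.1 covers metastatic disease, not adjuvant treatment.
- Exclusion 1.2 covers other cancers.
- Exclusion 1.8 could be used but names no treatment.
- Inclusion 1.4 requires a provider's written approval but does not tie it to completed treatment.
- The Clinical Characteristics paragraph has the chemotherapy plan obtained before randomization, with no eligibility rule attached.
- The Randomization paragraph includes a final eligibility check, which would apply the criteria as they stand.

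**Step 3: illustrate the effect on power for hs-CRP.** Inputs from the Power analysis section: SD 1.32 mg/L, correlation 0.8, reduction 0.71 mg/L, two-sided 5%.

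- SD of change = 1.32 × √(2 × (1 − 0.8)) = 0.835.
- d = 0.71 / 0.835 = 0.850.
- Plan's own figure: a two-sample t-test with 23 per arm (46 in total) gives 80.5%, which agrees with the stated 80%.
- Planned enrollment: 30 per arm (60 in total) gives 90.0%.

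Now assume that a share p of participants has twice the SD of change. The variance is multiplied by (1 − p) + 4p = 1 + 3p, so d becomes 0.850 / √(1 + 3p).

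| Assumed share p | 1 + 3p | d | Power, 30 per arm | Power, 29 per arm (about 3% dropout) |
|---|---|---|---|---|
| 0 | 1.00 | 0.850 | 90.0% | 88.9% |
| 5% | 1.15 | 0.793 | 85.5% | 84.3% |
| 10% | 1.30 | 0.746 | 81.1% | 79.7% |
| 20% | 1.60 | 0.672 | 72.6% | 71.1% |

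Neither p nor the doubled SD comes from the documents. The calculation is also on the untransformed change score, as in the plan's power statement, whereas the planned analysis is on log values with baseline adjustment.

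**The case against.** The strongest reply is that the intent is plain. The Objectives say that therapy is complete, and the phrase in 1.3 can be read as counting from resection or, where chemotherapy was given, from its end. Criterion 1.5 allows infusion-port removal, and the exercise section allows for neuropathy left over from chemotherapy; both fit a post-treatment population. In addition, the investigative team will have the medical history, concomitant medications, provider approval and chemotherapy plan before randomization, and can invoke exclusion 1.8.

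Much of this stands. A reader might infer from the wording that the trial means to enroll people on chemotherapy, or that nothing could prevent it. The documents support neither. What remains is that these safeguards are discretionary or carry no stated rule on current treatment, and that eligibility is first determined by yes-or-no questions in a phone screen. A criterion should give the intended answer when applied as written.

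A reader might also infer biased results or a clear loss of power. Randomization makes any imbalance in treatment status a matter of chance, not a systematic bias. On power, the same assumptions at 46 participants give 74.9%, 69.6% and 60.6%, but the trial enrolls 60. At 60, power stays above 80% up to a 10% share. In the other direction, the margin above 46 and 48 was set aside for dropout, crossover and recurrence, not for this.

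**Conclusion.** The point holds as a wording defect. In all four timing criteria the resection limb is sufficient, so read literally they admit a person whose chemotherapy is ongoing or ended less than 1 month ago. This contradicts the Objectives, and no exclusion names current treatment of the colorectal cancer. Radiotherapy is missing from every timing criterion except 3.2.

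This conclusion rests on the text alone and needs no assumption about numbers. The practical size is unknown, because the documents do not give the share of candidates affected or any effect of treatment on hs-CRP or IL-6. Under the assumed doubled SD, the loss of hs-CRP power at 60 participants is about 4 to 17 percentage points for shares of 5% to 20% (90.0 − 85.5 = 4.5; 90.0 − 72.6 = 17.4). Those figures illustrate and do not estimate. The correction is worth making because it is cheap and the mismatch bears on whom the result describes.

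**What to change.** Reconcile criteria 1.3, 2.2, 3.1 and 3.2 with the Objectives. For example, state that resection and any chemotherapy or radiotherapy given or planned for the colorectal cancer are all completed, with the existing interval counted from the last of them. The interval lengths need not change. The investigators should confirm that this is the rule they intend.

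The cost is a one-line amendment and a few candidates deferred until treatment ends. The chemotherapy plan needed to apply the rule is already obtained before randomization. If participants have already been randomized, check their treatment status at entry from those records and report any who were still on treatment or less than 1 month past it.
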